10.1.9. Laboratory Assessments

10.1.9.1. Clinical Laboratory Tests

Blood samples will be collected prior to dosing according to the SoA ([Table 1](#)).

All clinically significant laboratory abnormalities will be followed-up by repeat testing and further investigated per the judgment of the Investigator.

Specific tests are described below:

- **Hematology:** complete blood count with platelet count and standard indices will be obtained.
- **Chemistry:** sodium, potassium, chloride, carbon dioxide (CO₂), albumin, total protein, glucose, blood urea nitrogen (BUN), creatinine, uric acid, aspartate aminotransferase (AST), alanine aminotransferase (ALT), gamma-glutamyltranspeptidase (GGT), creatine phosphokinase (CPK), alkaline phosphatase, total bilirubin, direct bilirubin, lactate dehydrogenase (LDH), calcium, phosphorus and magnesium.
- **Coagulation Profile:** prothrombin time (PT) or international normalized ratio (INR), and partial thromboplastin time (PTT), also referred to as activated partial thromboplastin time (aPTT).
- **Urinalysis:** pH, glucose, protein, ketones, bilirubin, blood, urobilinogen, specific gravity, nitrite, and leukocytes by dipstick analysis or machine urinalysis. Urine microscopic examination will be performed if positive findings on dipsticks warrant further examination.

10.1.9.2. Virus Serology

At Screening approximately 8 mL of blood will be withdrawn into a plain vacutainer for standard serological tests for the presence of human immunodeficiency virus infection (HIV), hepatitis B virus infection (HBsAg), and hepatitis C virus infection (anti-HCV).

10.1.9.3. Urine Drug Screen

Urine screens will be conducted at Screening and at each CRU admission for drugs of abuse (at a minimum amphetamines, barbiturates, benzodiazepines, cannabinoids, cocaine, and opiates), alcohol, and cotinine. A positive result for drugs of abuse or alcohol, or cotinine levels indicative of active smoking at any time will result in subject exclusion from the study.

10.1.9.4. Pregnancy Testing and Contraception

Females of childbearing potential must not be pregnant and must have a negative serum pregnancy test result at the Screening Visit and negative urine pregnancy test on CRU admission days, with results known prior to initiating dosing; pregnancy testing will be monitored during the study.

Females of non-childbearing potential, defined as surgically sterile (status post hysterectomy, bilateral oophorectomy, or bilateral tubal ligation), or post-menopausal for at least 12 months (and confirmed with a screening FSH level in the post-menopausal range) do not require contraception during the study.

For females of childbearing potential, a highly reliable form of contraception must be used/practiced throughout the study and for 90 days following the study. Highly reliable acceptable forms of contraception include hormonal (i.e., oral, implantable, or injectable) and single-barrier method (i.e., condom), or an intrauterine device (IUD) and single-barrier method (i.e., condom) or vasectomized partner. True abstinence is acceptable only if it is the preferred and usual lifestyle of the subject.

It is not known if setmelanotide will affect spermatogenesis. Therefore, males with female partners of childbearing potential must agree to use contraception (e.g., if they have not had a vasectomy then should either (a) abstain from reproductive sexual intercourse or (b) use a highly reliable method such as condom and diaphragm with spermicide during intercourse) if they become sexually active during the study and for 90 days following the study. True abstinence is acceptable only if it is the preferred and usual lifestyle of the subject. Male subjects must not donate sperm for 90 days following their participation in the study.

In the event of pregnancy during setmelanotide treatment, setmelanotide is to be permanently discontinued.

If a pregnancy is reported, the Investigator should inform the Sponsor within 24 hours of learning of the pregnancy and should follow the procedures outlined in [Section 10.2.4](#).

Details of all pregnancies in female subjects and female partners of male subjects will be collected after the start of study treatment through 30 days after the last SC setmelanotide dose.

Note that pregnancy itself is not considered a serious adverse event (SAE). However, abnormal pregnancy outcomes (e.g., spontaneous abortion, fetal death, stillbirth, congenital anomalies, ectopic pregnancy) are considered SAEs.

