^b A comprehensive skin evaluation will be performed by the Investigator at Screening. If any concerning lesions are identified during the screening period, the subject should be referred to a dermatologist for assessment and potential biopsy and results should be confirmed as to whether the lesion is benign prior to first dose of setmelanotide. If the pre-treatment biopsy results are of concern, the subject will be excluded from the study.

^c Height will only be collected at Screening.

^d Supine blood pressure, supine heart rate, pulse rate, and tympanic (ear) body temperature. Heart rate and blood pressure will be measured using the same arm for each reading after the subject has been resting in the supine position for at least 5 minutes. For timepoints at which vital signs, PK blood samples, and/or ECGs are all to be collected, ECGs should be collected first followed by vital signs then PK samples, with the timing of the PK sample to occur at the nominal time.

^e Serum pregnancy test will be performed at Screening. Urine pregnancy test will be performed on all other designated days.

^f On the evening before continuous Holter ECG sampling, subjects will undergo a 10-hour overnight fast.

^g Breakfast is to be administered at approximately 7:00 AM every day in the CRU (30 minutes pre-dose). Lunch, dinner, and a snack will be administered at approximately 12:00 PM (after 4-hour assessments), 6:00 PM (after 10-hour assessments), and 9:00 PM, respectively.

^h **Group 1** will receive SC setmelanotide QD (approximately 7:30 AM) at a dose of 2 mg from Days 1 to 7; 3 mg from Days 8 to 10; 5 mg from Days 11 to 13; and 7 mg from Days 14 to 16.

Groups 2 and 3 will receive SC placebo QD (approximately 7:30 AM) from Days 1 through 16.

All doses will be double-blinded.

ⁱ **Group 1** will receive oral placebo with their SC setmelanotide dose on Days 10 and 16.

Group 2 will receive oral moxifloxacin 400 mg on Day 10 and oral placebo on Day 16.

Group 3 will receive oral placebo on Day 10 and moxifloxacin 400 mg on Day 16.

All doses will be double-blinded. On Days 10 and 16, subjects should receive SC setmelanotide/placebo first. Oral moxifloxacin/placebo should then be administered within 2 minutes of the SC dose.

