Subjects will remain in the CRU through the morning of Day 17 and will be discharged after completion of all study assessments if safety parameters are acceptable to the Investigator. Subjects will return to the CRU for a Follow-up visit 7 ± 2 days after receiving the last SC dose (Day 23 ± 2).

Adverse events (AEs), 12-lead safety ECGs, Columbia Suicide Severity Rating Scale (C-SSRS) score, clinical laboratory tests, vital signs, and concomitant medication monitoring will be collected throughout the study for safety assessments as described in the SoA ([Table 1](#)).

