5.5. Number of Subjects and Study Completion

This study is planned to enroll 72 subjects to achieve a total of 60 completed subjects ([Section 11.1](#)).

A subject is considered to have completed the study after completion of the Follow-up visit on Day 23 ± 2 .

Subjects who discontinue before completing the Follow-up visit are to attend a Treatment Discontinuation visit within 7 days (± 4 days) after the last SC dose for final study assessments. Subjects who discontinue the study early may be replaced, at the discretion of the Sponsor, in order to assure that the final sample size is large enough to maintain sufficient statistical power.

The end of the study is defined as the date of the last visit of the last subject under the auspices of the current study.

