6. SELECTION AND WITHDRAWAL OF SUBJECTS

6.1. Subject Inclusion Criteria

Subjects must meet all of the following criteria to be eligible for study participation:

1. Males or females between 18 and 50 years of age, inclusive.
2. Subject has body mass index (BMI) between 18.0 and 30.0 kg/m², inclusive.
3. Subject is in good health, as confirmed by no clinically significant findings from medical history, physical examination, 12-lead ECG, vital signs measurements, clinical laboratory evaluations, and liver function tests at Screening, Check-in (Day -2) and baseline (Day -1).
4. Female participants of childbearing potential must be confirmed non-pregnant and agree to use contraception ([Section 10.1.9.4](#)). Female participants of non-childbearing potential, defined as: surgically sterile (status post hysterectomy, bilateral oophorectomy, or bilateral tubal ligation), post-menopausal for at least 12 months (and confirmed with a screening follicle stimulating hormone [FSH] level in the post-menopausal lab range), do not require contraception during the study.
5. Male participants with female partners of childbearing potential must agree to use contraception (e.g., if not vasectomized, should either abstain from sexual intercourse or use a highly reliable method of contraception such as condom and diaphragm with spermicide during intercourse) if they become sexually active during the study or within 90 days following their participation in the study. Male subjects must also not donate sperm during and for 90 days following their participation in the study.
6. Subject is a nonsmoker (for at least 3 months) with negative urinary cotinine test at Screening and agrees to abstain from alcohol, recreational drugs (including marijuana), and tobacco- and nicotine-containing products for the duration of the study.
7. Subject is able to comprehend and is willing to sign an informed consent form and abide by the study restrictions.

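### The protocol does not require a reported pregnancy to be followed to its outcome; a lesser point is that planned pregnancy collection stops about 67 days before required contraception does

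*Protocol*

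**What the plan says.** Protocol Section 10.1.9.4 sets three rules that bear on this point.

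- **Contraception.** For females of childbearing potential, "a highly reliable form of contraception must be used/practiced throughout the study and for 90 days following the study". For males with partners of childbearing potential the duty applies "if they become sexually active during the study and for 90 days following the study". Inclusion criterion 5 (Section 6.1) words the male period slightly differently: "if they become sexually active during the study or within 90 days following their participation in the study".
- **Notice.** When a pregnancy is reported, "the Investigator should inform the Sponsor within 24 hours of learning of the pregnancy", and the reader is sent to Section 10.2.4 for the procedure.
- **Collection.** Details of pregnancies in female subjects and in female partners "will be collected after the start of study treatment through 30 days after the last SC setmelanotide dose".

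The same section states that pregnancy is not itself an SAE but that abnormal outcomes, such as stillbirth or a congenital anomaly, are. Section 10.2.5 records SAEs through the Follow-up visit. After a subject completes the study, it requires a report only of SAEs that the Investigator considers related to study drug.

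On timing, Section 5.1 says "Subjects will return to the CRU for a Follow-up visit 7 ± 2 days after receiving the last SC dose", and Section 5.5 says "A subject is considered to have completed the study after completion of the Follow-up visit". SAP Section 4.11.3 lists pregnancy test results and adds no follow-up rule.

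**The concern.** What matters for safety about an exposed pregnancy is how it ends. The protocol recognises this by classing abnormal outcomes as SAEs, but for a conception during or soon after the trial those outcomes mostly arise long after SAE recording has closed. No stated duty carries the pregnancy from the first notice to its end. The Sponsor could therefore hold a report of a pregnancy exposed to its marketed product and have no recorded outcome.

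The length of the collection window is a lesser matter. The protocol sets 90 days after the study as its precaution period, and for males it gives the reason that an effect on spermatogenesis is unknown. Planned collection stops well inside that period.

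Only safety reporting is at stake. The QTc model, the PK summaries and the assay-sensitivity test are unaffected.

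**Working it through.** **1. Trace a reported pregnancy through the protocol.**

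- Section 10.1.9.4: the Sponsor is notified within 24 hours; then follow Section 10.2.4.
- Section 10.2.4: describes AE and SAE reporting and does not mention pregnancy. It allows the Sponsor to ask for follow-up information, but on an SAE.
- Section 10.1.9.4 again: an ongoing pregnancy is not an SAE. The rule in Section 10.2.5 that SAEs are followed until resolution therefore does not attach to it.
- Section 10.2.5: an abnormal outcome is recorded as an SAE if it occurs by the Follow-up visit. After completion it must be reported only if judged related.

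Two groups of outcomes remain with no duty to capture them: normal outcomes, and abnormal outcomes after completion that are judged unrelated.

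**2. Check the protocol's own Follow-up day.** The last SC dose is on Day 16. In Group 1 the 7 mg doses run from Day 14 to Day 16 (Table 1, footnote h), and Groups 2 and 3 "will receive SC placebo QD (approximately 7:30 AM) from Days 1 through 16". Follow-up = 16 + 7 ± 2 = Day 23 ± 2 (Days 21 to 25), which matches the protocol.

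**3. End of each period.**

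- Collection: 16 + 30 = Day 46.
- Contraception: 23 + 90 = Day 113 (21 + 90 = 111; 25 + 90 = 115).
- Difference: 113 − 46 = 67 days (111 − 46 = 65; 115 − 46 = 69).
- If the 90 days are counted from the last dose instead: 16 + 90 = Day 106, and 106 − 46 = 60 days.
- If a subject leaves early, the Treatment Discontinuation visit is 3 to 11 days after the last dose. Contraception then ends 93 to 101 days after that dose, and the difference is 93 − 30 = 63 to 101 − 30 = 71 days.

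**4. Collection against SAE recording.** 46 − 23 = 23 days (46 − 25 = 21; 46 − 21 = 25). On Days 24 to 46 a pregnancy is inside planned collection, but an abnormal outcome judged unrelated need not be recorded as an SAE.

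**5. When outcomes would fall.** The documents give no gestation figure, so assume 245 to 280 days from conception to term birth. Completers are confined from Day −2 until discharge on Day 17, so take conception from Day 17.

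- Earliest term birth: 17 + 245 = Day 262, which is 262 − 46 = 216 days after collection ends.
- Conception on Day 46, longest gestation: 46 + 280 = Day 326, which is 326 − 46 = 280 days after.

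**6. Scale.** About 72 / 3 = 24 subjects are planned to receive setmelanotide. The documents give no pregnancy rate, so these are calendar days and not a share of pregnancies.

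**The case against.** The strongest reply is that the protocol already has several open routes and that few events will use them.

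- The 24-hour notice has no end date and no causality test, so a pregnancy that the site learns of on Days 47 to 113 still reaches the Sponsor.
- The cross-reference to Section 10.2.4 can be read as importing its procedures, including a narrative and follow-up on request.
- Section 10.2.5 tells the Investigator to follow subjects proactively at later visits or contacts after an AE or SAE report.
- A related abnormal outcome is reportable at any time.
- Contraception is mandatory, subjects are confined for most of the trial, and the removed consent pages may cover partner consent or outcome follow-up.

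All of this stands as mitigation. It narrows the gap but does not close it. The notice conveys that a pregnancy exists, not how it ended, and the follow-up provisions depend on an AE or SAE report. The relatedness test is also a weak safeguard here. Section 10.2.2 makes a known response pattern part of both the possible and the probable grade, so an outcome with no established pattern could be graded lower.

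A reader might infer four stronger things that the documents do not support.

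- *The two periods must match.* No passage says so. Thirty days is a stated choice, and the protocol gives no exposure-based reason that shows it is too short.
- *Pregnancies after Day 46 are lost.* The open-ended notice and the rule on related SAEs contradict this.
- *No term birth can fall inside collection.* A partner already pregnant at entry is not excluded and could deliver by Day 46.
- *Placebo subjects are outside collection, because the sentence names the last setmelanotide dose.* All groups have the same SC schedule under a double blind, so this is a wording matter only.

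**Conclusion.** The point holds as a low-cost improvement in safety reporting that should be made.

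The main finding is that the supplied text imposes no duty to obtain the outcome of a reported pregnancy. If the collection sentence only defines which pregnancies qualify, with details allowed later, that duty is still missing. The finding covers only the text available for review.

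The window difference is secondary. It is 67 days (65 to 69) for a completer, 60 if counted from the last dose, and 63 to 71 for a subject who leaves early. The Day 46 and Day 113 dates assume that the last dose is given on Day 16 as planned; a delayed or stopped dose moves them. The margin of at least 216 days to a term birth rests on the assumed 245 to 280 days and on conception from Day 17. The finding is not sensitive to the exact gestation figure.

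**What to change.** In order of value:

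1. In Section 10.1.9.4 add: *Reported pregnancies will be followed to outcome, normal or abnormal, with the partner's agreement where the pregnancy is in a partner.*
2. In Section 10.2.5 add: *Abnormal outcomes of collected pregnancies are reported to the Sponsor's safety reporting as SAEs whenever they occur, regardless of causality; database lock is not held for them.*
3. As a second step, end collection in Section 10.1.9.4 at *90 days after the end of study participation (Follow-up or Treatment Discontinuation visit)*. If a dose-based end is kept, refer to the last SC dose so that the wording fits all groups.

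The cost is protocol wording with no added visit. Item 3 lengthens passive reporting by about 67 days. Items 1 and 2 mean contact with the few subjects or partners who report a pregnancy until its outcome. With the longer window this could last until about Day 393 (113 + 280, on the assumed gestation), well after a subject's last visit. Partner consent wording may also be needed.

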10.2. Adverse Events

10.2.1. Definition of Adverse Events and Serious Adverse Events

10.2.1.1. Adverse Event

An AE is any untoward medical occurrence associated with the use of a drug in humans, whether or not considered drug related. An adverse event (also referred to as an adverse experience) can be any unfavorable and unintended sign (e.g., an abnormal laboratory finding), symptom, or disease temporally associated with the use of a drug, without any judgment about causality. An AE can arise from any use of the drug (e.g., off-label use, use in combination with another drug) and from any route of administration, formulation, or dose, including an overdose.

10.2.1.2. Serious Adverse Event

An AE or suspected adverse reaction is considered an SAE if, in the view of either the Investigator or Sponsor, it results in any of the following outcomes:

- Death.
- Life-threatening. Life-threatening means that the subject was at immediate risk of death from the reaction as it occurred, ie, it does not include a reaction which hypothetically might have caused death had it occurred in a more severe form.
- In-patient hospitalization or prolongation of existing hospitalization. Hospitalization admissions and/or surgical operations scheduled to occur during the study period but planned prior to study entry are not considered AEs if the illness or disease existed before the subject was enrolled in the study, provided that it did not deteriorate in an unexpected manner during the study (eg, surgery performed earlier than planned).
- A persistent or significant incapacity or substantial disruption of the ability to conduct normal life functions.
- Congenital anomaly/birth defect.
- Important medical event. An important medical event is an event that may not result in death, be life-threatening, or require hospitalization but may be considered an SAE when, based upon appropriate medical judgment, it may jeopardize the subject and may require medical or surgical intervention to prevent one of the outcomes listed in the definitions for SAEs. Examples of such medical events include allergic bronchospasm requiring intensive treatment in an emergency room or at home, blood dyscrasias or convulsions that do not result in in-patient hospitalization, or the development of drug dependency or drug abuse.

10.2.1.3. Unexpected Adverse Drug Reaction

An unexpected adverse drug reaction (ADR) is a reaction for which the nature or severity is not consistent with the product information (i.e., [IMCIVREE \(setmelanotide\) Prescribing Information \(2020\)](#)). Until product information is amended, expedited reporting is required for additional occurrences of the reaction. Reports that add significant information on specificity or severity of a known, already documented SAE constitute unexpected events. For example, an

event more specific or more severe than described in product label would be considered “unexpected”.

10.2.2. Relationship to Study Drug

Relationship to study drug administration (setmelanotide or moxifloxacin, assessed separately) will be determined by the Investigator according to the following criteria.

- **None:** No relationship between the event and the administration of study drug. The event is related to other etiologies, such as concomitant medications or subject’s clinical state.
- **Unlikely:** The current state of knowledge indicates that a relationship to study drug is unlikely, the temporal relationship is such that study drug would not have had any reasonable association with the observed event or another reasonable explanation for the event (e.g., a pre-existing clinical condition or other concomitant treatment) is more likely.
- **Possible:** A reaction that follows a plausible temporal sequence from administration of the study drug and follows a known response pattern to the suspected study drug. The reaction might have been produced by the subject’s clinical state or other modes of therapy administered to the subject.
- **Probable:** A reaction that follows a plausible temporal sequence from administration of the study drug and follows a known response pattern to the suspected study drug. The reaction cannot be reasonably explained by the known characteristics of the subject’s clinical state or other modes of therapy administered to the subject.

For the purpose of safety analyses, all AEs that are classified as possible or probable will be considered treatment-related events.

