3.1.2. Setmelanotide

Setmelanotide (also known as RM-493) is a synthetic, cyclic octapeptide (8-amino acid-containing peptide) that functions as a potent MC4R agonist. Setmelanotide is an 8-amino acid, cyclic peptide that binds with high affinity (inhibitory constant $[K_i] = 2.1$ nM) to the human MC4R and is efficient in activating MC4R (50% effective concentration $[EC_{50}] = 0.27$ nM). Setmelanotide is indicated for chronic weight management in adult and pediatric patients 6 years of age and older with obesity due to POMC, PCSK1, or LEPR deficiency confirmed by genetic testing demonstrating variants in *POMC*, *PCSK1*, or *LEPR* genes that are interpreted as pathogenic, likely pathogenic, or of uncertain significance ([IMCIVREE \(setmelanotide\) Prescribing Information 2020](#)).

Setmelanotide was evaluated extensively in nonclinical studies for cardiovascular parameters, primarily because of the potential concern for effects on blood pressure (BP) and heart rate (HR). The IC_{50} for the effect of setmelanotide on human ether-à-go-go-related gene (hERG) potassium current was estimated to be greater than 300 μ g/mL, the maximum concentration tested. In addition, an extensive, multi-day cardiovascular telemetry study with setmelanotide administered by subcutaneous (SC) continuous infusion was performed in cynomolgus monkeys. No setmelanotide-related effects were noted on the electrocardiogram (ECG) parameters (PR, QRS, QT, and QTc intervals) following the administration at doses of 2.5, 12, and 25 mg/kg/day. In both these studies, there were extremely large exposure/concentration margins to the approximate Cmax of the maximum therapeutic 3 mg SC injection dose (~40.0 ng/mL) and the anticipated Cmax of the supratherapeutic 7 mg SC injection dose (~93.3 ng/mL, assuming dose proportionality).

QTc evaluations were additionally conducted in 3 initial Phase 1 and Phase 2 clinical studies, as well as in 57 patients with monogenic obesity in 3 Phase 2 and Phase 3 studies. Mean and median data for QTcF demonstrate no effect of setmelanotide on QTc interval at doses up to 3 mg QD.

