10.2.4. Procedures for AE and SAE Reporting

Each subject must be carefully monitored for the development of any AEs. This information should be obtained in the form of non-leading questions (e.g., “How are you feeling?”) and from signs and symptoms detected during each examination, observations of study personnel, and spontaneous reports from subjects.

All AEs (serious and non-serious) spontaneously reported by the subject and/or in response to an open question from study personnel or revealed by observation, physical examination, or other diagnostic procedures will be recorded on the appropriate eCRF. Any clinically relevant deterioration in laboratory assessments or other clinical findings is considered an AE and must be recorded on the appropriate eCRF. When possible, signs and symptoms indicating a common underlying pathology should be noted as one comprehensive event.

All SAEs that occur during the study must be reported by the Investigator to the Medical Monitor within 24 hours from the point in time when the Investigator becomes aware of the SAE. All SAEs must be reported whether or not considered causally related to the study drug. SAE forms will be completed, and the information collected will include subject number, a narrative description of the event, and an assessment by the Investigator as to the severity of the event and relatedness to study drug. Follow-up information on the SAE may be requested by the Sponsor or its designee.

If there are serious, unexpected adverse drug reactions associated with the use of the study drug, the Sponsor or designee will notify the appropriate regulatory agency(ies), Independent Ethic Committees (IECs) and all participating investigators on an expedited basis. It is the responsibility of the Investigator to promptly notify the Institutional Review Board (IRB)/IEC where required by the IRB/IEC of all unexpected serious adverse drug reactions involving risk to human subjects.

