10.2.5. Adverse Event Monitoring and Follow-up

Monitoring of AEs will be conducted throughout the study. AEs will be recorded in the eCRFs from Screening through the Follow-up visit. AEs that occur after the start of study drug administration will be considered treatment-emergent adverse events (TEAEs). SAEs will be recorded through the Follow-up visit. All AEs should be monitored until they are resolved.

After the initial AE/SAE report, the Investigator is required to proactively follow each subject at subsequent visits/contacts. All SAEs will be followed until resolution, stabilization, the event is otherwise explained, or the subject is lost to follow-up.

Any SAE that occurs at any time after completion of the study, which the Investigator considers to be related to study drug, must be reported to the Sponsor or designee.

In the event a subject is withdrawn from treatment due to an AE, the subject should be encouraged to complete the final study/early termination visit to monitor the event to resolution and obtain additional protocol defined safety assessments.

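### Protocol 10.2.2 makes a known response pattern a condition of both related causality grades, so a well-timed reaction of a new kind to setmelanotide cannot be graded related

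*Protocol*

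**What the plan says.** Protocol 10.2.2 states that relationship, rated separately for setmelanotide and moxifloxacin, "will be determined by the Investigator according to the following criteria". There are four grades.

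- **None:** no relationship; the event is put down to other causes.
- **Unlikely:** present knowledge makes a relationship unlikely, or the timing does not fit, or another explanation is more likely.
- **Possible** and **Probable:** both open with the same two requirements: plausible timing after the study drug, and a reaction that "follows a known response pattern to the suspected study drug". They differ only in whether the subject's condition or other treatment could explain the event.

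The section closes by saying that, for safety analyses, "all AEs that are classified as possible or probable will be considered treatment-related events".

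These other provisions bear on the point:

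- Protocol 10.2.1.3 defines an unexpected adverse drug reaction as "a reaction for which the nature or severity is not consistent with the product information".
- Protocol 10.2.4 sets out expedited notification by the sponsor or its designee, beginning "If there are serious, unexpected adverse drug reactions associated with the use of the study drug".
- Protocol 10.2.5 says that an SAE after study completion "which the Investigator considers to be related to study drug, must be reported to the Sponsor or designee".
- Protocol 3.1.2 says of the earlier clinical data: "Mean and median data for QTcF demonstrate no effect of setmelanotide on QTc interval at doses up to 3 mg QD".
- Protocol 5.2.4 and SAP 3.2.4 make adverse events, assessed for relation to each drug, a safety endpoint. SAP 4.11.1 tabulates all TEAEs by relationship.

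**The concern.** A causality scale should allow a reaction that nobody has seen before to be called drug-related. This one appears not to. Timing and a known pattern are joined as two conditions, and the second excludes anything new.

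That matters more than usual here. The study gives 5 and 7 mg, above the 3 mg that Protocol 5.4 calls the maximum therapeutic dose. It also exists to ask about an effect on QT that, according to Protocol 3.1.2, has not been seen at doses up to 3 mg. Moxifloxacin, by contrast, is expected to prolong QTcF, with a peak of 10 to 15 msec (Protocol 3.2). The investigator grades both drugs without knowing which was given (Protocol 7.5). For a QT event, the pattern condition therefore points to moxifloxacin and away from setmelanotide, whatever the subject received.

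At stake are the relationship breakdown within a stated safety endpoint, the count of treatment-related events, and any reporting rule that turns on the investigator's opinion of relatedness.

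**Working it through.** The point rests on definitions, so there is no figure to reproduce. The check passes one test event through each grade and then follows the result to each place where a grade is used.

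**Test event.** An adverse event that starts soon after a setmelanotide dose, has no other explanation, and is of a kind not previously associated with the drug.

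| Grade | Requirement | Does the event meet it? |
|---|---|---|
| Probable | plausible timing, known pattern, not explained by other causes | No: fails the known pattern |
| Possible | plausible timing, known pattern, other causes may explain it | No: fails the known pattern |
| Unlikely | knowledge points against, or timing does not fit, or a better explanation exists | Timing fits and there is no better explanation; only the appeal to present knowledge could apply, and absence of knowledge is not evidence against |
| None | other causes account for it | No: there are none |

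Both related grades are closed, and neither remaining grade clearly fits. The scale has a gap. The investigator must either use a non-related grade or set the wording aside.

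**A QT event attributed to setmelanotide.** Protocol 3.1.2 reports no QTc effect up to 3 mg, so these documents describe no QT response pattern for setmelanotide. Group 1 takes oral placebo on Days 10 and 16, while Groups 2 and 3 each take moxifloxacin on one of those days. A blinded investigator who sees a QT event on either day in a Group 1 subject finds the pattern condition met only for moxifloxacin, which that subject did not receive. Before Day 10 no oral product has been given, so a QT event then would have no related grade for either drug.

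**Unexpected reactions.** Protocol 10.2.1.3 covers reactions unexpected in nature or in severity. One unexpected only in severity can still follow a known pattern and be graded related. One unexpected in nature generally cannot. Sections 10.2.1.3 and 10.2.4 thus assume a kind of reaction that the grades in 10.2.2 cannot express.

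**Where the grade is used.**

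| Output or rule | Effect on the test event |
|---|---|
| Treatment-related count (Protocol 10.2.2) | Lost |
| TEAE table by relationship (SAP 4.11.1) | Present, in a non-related row |
| Overall TEAE table, severity table, full listing (SAP 4.11.1) | Present |
| SAP rule for missing causality (worst case) | Does not help: the grade is recorded, not missing |
| In-study SAE report to the Medical Monitor (Protocol 10.2.4) | Unaffected: required whatever the causality |
| SAE after study completion (Protocol 10.2.5) | Exposed: depends on the investigator's view |
| Expedited notification (Protocol 10.2.4) | At risk only if the investigator's grade decides what counts as a drug reaction, which the text does not say |
| C-QTc model, decision rule, Holter outlier and morphology tables (SAP 4.10.2 and 4.10.3) | Unaffected: no causality grade is used |

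**Scope.** About 72 subjects randomized 1:1:1 gives 72 / 3 = 24 planned on setmelanotide. The documents give no expected number of adverse events of a new kind, so the number misclassified cannot be estimated.

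**The case against.** The strongest reply is that little depends on the grade. The primary question is answered from Holter data by concentration and treatment. Safety receives no formal statistical analysis (Protocol 11.3.4). In a randomized, placebo-controlled study, adverse event rates by group can show a drug effect without anyone grading causality. SAEs during the study reach the Medical Monitor regardless of the grade. All of this stands, and it limits the consequences.

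A second reply is that the protocol does not define a known response pattern. The term could take in pharmacology and the Investigator's Brochure as well as the label. That also stands: not every unlabelled event is excluded. A truly new reaction still fails on any reading of known.

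A reader might infer more than the text supports in three ways.

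- **That such events disappear from a table of related events.** The SAP describes no related-only table. The event remains in the by-relationship table, in the wrong row.
- **That no QT event can be graded related.** One on Day 10 or 16 can be graded related to moxifloxacin and would then count as treatment-related. The gap concerns attribution to setmelanotide.
- **That expedited reporting fails.** Protocol 10.2.4 does not name the grades as its trigger, and 10.2.2 limits the Possible and Probable rule to safety analyses. The link is an inference. The same section does, however, put the SAE relatedness assessment and prompt IRB/IEC notification in the hands of the investigator, who grades under 10.2.2.

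**Conclusion.** The defect is real and lies in the wording. As written, 10.2.2 gives no related grade to a well-timed reaction of a new kind, including a QT or arrhythmia adverse event attributed to setmelanotide. The certain effect is misclassification within a stated safety endpoint and loss from the treatment-related count. The plausible further effect is a missed report of an SAE after study completion. The text also conflicts with 10.2.1.3 and 10.2.4.

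Severity is moderate. The QT conclusion and in-study SAE reporting to the Medical Monitor do not rest on the grade. The verdict assumes that sites apply the definitions as written and that a known pattern means one already established for that drug. Investigators may use broader judgement in practice, but the scale should not depend on their departing from its text.

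**What to change.** In Protocol 10.2.2, make a known response pattern a supporting factor instead of a required condition:

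- a plausible time course supports Possible;
- a plausible time course that other causes do not reasonably explain supports Probable.

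Keep the rule that both grades count as treatment-related. Align 10.2.1.3, 10.2.4 and 10.2.5 with the revised grades, so that a reaction unexpected in nature can be recorded as related and it is clear whose causality assessment each reporting rule uses. Carry the same wording into the eCRF completion guidance. The SAP tables need no change.

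The cost is a short protocol wording change and site guidance. The downside is that a few more adverse events will be graded related, in placebo subjects as well, because grading is blinded. Tabulation by treatment group puts these in context.
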